### 13.1.1 Primary Endpoint

The primary endpoint for this trial is the objective response rate, defined as the proportion of patients who have had a partial response (PR) or complete response (CR) within the first 6 months after initiation of therapy with trametinib. All eligible patients who have received at least one dose of the study regimen will be evaluable for response. Participants will be re-evaluated for response every 2 cycles (8 weeks). Response, stable disease and progression will be evaluated using the international criteria proposed by the Response Evaluation Criteria in Solid Tumors (RECIST) version 1.1 guideline. In addition to a baseline scan, confirmatory scans will be obtained after approximately 8 weeks following initial documentation of a clinical benefit.

In determining this rate, the number of patients with RECIST 1.1 based PR or CR will be divided by the number of evaluable patients. All evaluable patients will be used for this analysis. Evaluable patients will be defined as only those participants who have received at least one cycle of therapy, and have had their disease re-evaluated. Exact binomial 95% confidence intervals for the true PR+CR response rate will be calculated.

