### 13.3. Study design, primary endpoint analysis plans and power:

To test these hypotheses, we propose a single arm, two-stage phase II trial of single agent trametinib in advanced TNBC patients, followed by trametinib in combination

with AKT inhibitor GSK2141795 at time of tumor progression (Figure 1, [Schema](#)). This design was chosen because trametinib monotherapy is more tolerable than trametinib in combination with GSK2141795, and therefore, it is vital to first assess if there is a subpopulation of TNBC patients (such as those that are PTEN wild type) that will derive benefit from anti-MEK therapy alone before exposing patients to dual MEK and AKT inhibition. GSK2141795 will be added at time of tumor progression to determine if the addition of AKT inhibition will overcome the primary proposed mechanism of resistance to trametinib through blockade of the PI3K/AKT pathway.

The goals of this study are to evaluate whether or not trametinib alone provides sufficient clinical response in this patient population (Part 1), and to evaluate if the combination of trametinib plus GSK2141795 in patients who progress will improve the objective response in this patient population (Part 2). To minimize the expected number of subjects treated if the trametinib monotherapy is not sufficiently active in this setting, a Simon two-stage Optimum Design will be used for Part 1 that allows for early termination of accrual if insufficient activity with monotherapy is observed. In addition, upon completion of Part 1 of this study we will further evaluate the combination of trametinib plus GSK2141795 in those patients in Part 1 who progress (Part 2). Similarly, to limit the number of patients accrued if this combination regimen proves to be insufficiently active, we will utilize a Fleming Two-Stage Design. As in any two-stage design, the 2nd stage will only commence and accrue additional patients if the specified decision criteria are met for the 1st stage. Even though Part 2 is directly linked to Part 1 (in the fact that those who progress on Part 1 are able to go on to Part 2) each part will have its own study design and decision criteria associated with them. The primary evaluation and goal of interest is Part 1, where the Part 2 evaluation is a secondary goal of this trial.

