For Part 1: We hypothesize that the true ORR with monotherapy is at least 20% versus a null hypothesis that the ORR is at most 5%, reflecting that any treatment success (clinical response) is due to chance alone. Under this Simon Optimal two-stage design, we aim to test the null hypothesis  $H_0: \text{ORR} \leq 5\%$  vs.  $H_1: \text{ORR} \geq 20\%$  to evaluate the efficacy of trametinib monotherapy. With 90% power and a Type I error rate of 10%, the interim analysis for this design requires that at least one patient of the first 12 evaluable patients enrolled have observed objective response (CR+PR); otherwise, if no patients have an objective response to treatment, then we will consider this sufficient early evidence that this treatment regimen is not worth pursuing further as monotherapy. At this point, we will evaluate the combination regimen in Part 2 in any patients subsequently enrolled on the trial and not just those who fail monotherapy in Part 1. If at least 1 patient has clinical response out of the first 12 enrolled patients treated with combination therapy, we will continue accrual to the second stage and accrue an additional 25 patients for a total of 37 patients. In the final analysis, we would need to see at least 4 patients with clinical response as defined above out of the first 37 evaluable patients accrued to determine that this monotherapy has promising associated activity and thus is worth pursuing further. Otherwise, if 3 or fewer have clinical benefit, then we will consider this monotherapy to not be sufficiently active on its own.

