For Part 2: In this part of the trial, we will focus on evaluating the ability to obtain clinical response in those patients in Part 1 who progress on monotherapy; we expect that about 80% of patients will progress and remain free of limiting toxicity to go on to Part 2. With our planned over-accrual and if all are evaluable, we will have 32 patients available for this portion of the trial. If we observe issues with patients going off study during Part 1, the study team will discuss with CTEP potential solutions and if patients who cannot tolerate the MEK inhibitor as single agent therapy will be replaced in the overall sample size to facilitate subsequent evaluation of the combination regimen in Part 2. However, in evaluation of the primary outcome of the MEK inhibitor as single agent therapy, any such patient who is unable to tolerate therapy and/or goes off study during Part 1 will still be included in the analyses and decision rule evaluations.

Since this is also a relapsed/refractory setting, our goals are the same as those in Part 1. Therefore, we hypothesize that the objective response rate of this combination therapy is at least 20% versus the null hypothesis that it is at most 5%. With 90% power and a Type I error rate of 10%, this Fleming two-stage design has an interim analysis after the first 16 evaluable patients are accrued. If no patients have documented objective response (CR+PR) out of the first 16 enrolled patients the trial cohort then we will consider this sufficient early evidence that this is not a promising regimen and accrual will be terminated. If at least 1 patient has clinical response out of the first 16 enrolled patients, then accrual will continue and an additional 16 patients will be accrued for a total 32 evaluable patients. In the final analysis, if at least 4 patients have clinical response as defined above, then we will consider this a promising regimen and worthy of further study.

Assuming that the number of responses is binomially distributed, we will estimate objective response rates independently for parts 1 and 2, and generate corresponding 95% binomial confidence intervals.

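### The planned 95% response-rate intervals treat the sample size as fixed, so they are not exact under either two-stage design, and their level does not match the one-sided 10% decision rule

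*Combined protocol and SAP*

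**What the plan says.** Section 13.3 describes Part 1 as a two-stage trial: "a Simon two-stage Optimum Design will be used for Part 1 that allows for early termination of accrual". The hypotheses are a response rate of at most 5% against at least 20%, with type I error 10% and power 90%. Accrual stops if none of the first 12 evaluable patients responds; otherwise it goes on to 37. For a positive result, "we would need to see at least 4 patients with clinical response". Part 2 uses a Fleming two-stage design with the same hypotheses and error rates: stop at 0 of 16, otherwise continue to 32, and call the regimen promising at 4 or more responses.

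Section 13.1.1 defines the estimate as responders divided by evaluable patients and adds: "Exact binomial 95% confidence intervals for the true PR+CR response rate will be calculated". For both parts, section 13.3 treats the number of responses as binomial and will "generate corresponding 95% binomial confidence intervals". Section 13.5.2 repeats the 95% level. No section adjusts the interval for the futility stop, gives an interval at the level of the test, or says how to read a positive decision when the interval contains 5%.

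**The concern.** Two separate things are wrong.

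- **Method.** A trial that stops at 0/12 and otherwise goes on to 37 does not produce a binomial count with fixed n. The fixed-n interval therefore does not have the exact property that section 13.1.1 claims for it.
- **Level.** A two-sided 95% interval puts 2.5% in each tail, while the decision rule spends 10% in one tail. At the lowest counts that pass, the report would call the treatment worth pursuing next to an interval that does not exclude the null rate.

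At stake are the error bars on the primary endpoint and a clear reading of a marginal positive result. If nothing is settled in advance, somebody must choose between conflicting summaries after seeing the data.

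**Working it through.** **Inputs (section 13.3).** p0 = 5%, p1 = 20%. Part 1: n1 = 12, stop at 0, N = 37, success at 4 or more. Part 2: n1 = 16, stop at 0, N = 32, success at 4 or more. The text does not call the 10% one-sided. That follows from the form of the hypotheses and from a success rule with only a lower bound on responses.

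**Step 1: reproduce the design.** P(success) = Σ over x1 ≥ 1 of b(x1; 12, p) × P[Bin(25, p) ≥ 4 − x1].

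- At p = 5%: 0.3413×0.1271 + 0.0988×0.3576 + 0.0173×0.7226 + 0.0022 = 0.0935.
- At p = 20%: 0.2062×0.9018 + 0.2835×0.9726 + 0.2362×0.9962 + 0.2054 = 0.902.

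Part 1 meets its stated 10% and 90%. Without the futility stop, P[Bin(37, 5%) ≥ 4] = 0.112, which is over 10%. The same formula for Part 2 gives 0.071 and 0.896.

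**Step 2: intervals.** The planned interval is Clopper-Pearson with n fixed. For the two-stage interval, outcomes are ordered by stage and then by responses. The lower limit solves P(continue and S ≥ s) = a/2, and the upper limit solves P(stop, or continue and S ≤ s) = a/2. Because the only stopping outcome is zero responses, ordering by observed rate gives the same order.

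| Result | Planned 95% | Two-stage 95% | Fixed-n 80% | Two-stage 80% |
|---|---|---|---|---|
| 4/37 | 3.0–25.4% | 3.2–28.5% | 4.8–20.5% | 5.1–22.0% |
| 5/37 | 4.5–28.8% | 4.7–30.5% | 6.7–23.6% | 7.0–24.6% |
| 6/37 | 6.2–32.0% | 6.3–33.0% | 8.8–26.7% | 8.9–27.3% |
| 4/32 | 3.5–29.0% | 3.6–29.3% | 5.6–23.4% | 5.6–23.6% |
| 5/32 | 5.3–32.8% | 5.3–32.9% | 7.8–27.1% | 7.8–27.1% |

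The planned upper limit at 4/37 shows the effect. At p = 25.4%, P[Bin(37) ≤ 4] = 0.025 as intended, but under the design P(stop, or S ≤ 4) = 0.049.

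**Step 3: coverage of the planned interval under the design.** Coverage is summed over all outcomes, for true rates from 1% to 60%.

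- Part 1 is worst just above 26.46%, the upper limit for 0/12. Missed there: the stop at 0/12 (0.0250), 1 to 4 of 37 (0.0138), and 16 or more of 37 (0.0201). Coverage is 1 − 0.0589 = 94.1%, and the upper-limit miss is 0.0388 against a nominal 0.025.
- Part 2 is worst just above 20.8%: 1 − 0.0239 − 0.0172 − 0.0226 = 93.6% (about 93.7% at a true rate of 21%).
- At 5% and 20%, Part 1 coverage is 99.1% and 97.0%.

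**Step 4: which cause produces the overlap with 5%?**

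- At 4/37, the two-stage 95% interval (from 3.2%) and the fixed-n 80% interval (from 4.8%) both still contain 5%. Only both changes together exclude it (5.1%).
- At 5/37 the level alone is enough (6.7%), and so it is at 4/32 (5.6%). The stage adjustment alone is not enough at either.

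**Step 5: how often it would arise.** Given a positive Part 1, the chance of exactly 4 or 5 responses is 90% if the true rate is 5% ((0.0614 + 0.0232)/0.0935), 66% if it is 10%, and 17% if it is 20%.

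**The case against.** The decision is a count, and no section uses the interval to decide. Any rule run at one-sided 10% will yield marginal successes whose 95% interval covers the null; that is honest uncertainty, not a contradiction. Coverage near 94% at worst, and above 95% at both design rates, is close to nominal. Part 2 limits hardly move. Section 13.2 also describes accrual in the past tense, so a new primary estimator would come late in an open-label trial.

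All of this stands as a limit on the weight of the point. It does not make the interval exact, and the plan still gives no reading of a positive result beside an interval that contains 5%.

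Three stronger inferences are tempting, and the documents do not support them:

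- **That ignoring the futility stop causes the overlap with 5%.** The two-stage 95% intervals contain 5% at 4/37 and 5/37 as well.
- **That the test or its error rates are faulty.** They follow from the counts and do not depend on how the interval is built.
- **That the uniformly minimum variance unbiased estimate (UMVUE; 13.4% at 4/37, against 10.8%) should become primary because the simple proportion is biased downward.** The mean proportion is indeed 3.2%, 8.1% and 19.1% at true rates of 5%, 10% and 20%. But that average includes the early stops; given continuation it is 6.9%, 11.3% and 20.5%. Root mean squared error for the proportion against the UMVUE is 4.5 against 5.6 points at 5%, and 8.1 against 7.7 at 20%. This is a trade-off, not a correction.

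**Conclusion.** The point holds as a matter of interval reporting. The planned intervals are not exact under either design. Coverage can fall to about 94.1% (Part 1) and 93.6% (Part 2), and the upper limit at 4/37 is 3.1 points too low (28.5 − 25.4). The mismatch of level is separate. It leaves 5% inside the 95% interval for a positive 4/37, 5/37 or 4/32, and the stage adjustment changes agreement with the decision only at 4/37, by 0.3 points on the 80% lower limit (5.1 − 4.8). Decisions, error rates and patients are not affected.

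Assumptions: the 10% is one-sided, and the analysed numbers are exactly 12 + 25 and 16 + 16. Section 13.2 also mentions a decision analysis on the first 45 evaluable patients and estimates from all evaluable patients. That is a separate inconsistency, and these figures would change with another denominator.

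**What to change.** In sections 13.1.1 and 13.3:

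1. Keep responders over evaluable patients as the primary point estimate. The UMVUE may be supplementary only.
2. Replace the fixed-n interval with a two-stage exact 95% interval, ordered by stage and then responses, for each part. Name the patients it covers (the first 37 and the first 32 evaluable).
3. Add the two-sided 80% two-stage interval, whose lower limit is the one-sided 90% bound that matches the test.
4. State that the decision rests on the response count, and that a 95% interval containing 5% beside a positive decision reflects the stricter level and does not reverse the decision.

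The cost is SAP wording, a little more analysis work and a slightly higher upper limit; no patients are added. Since accrual is described as past, date the change and note that the method follows from the design alone.

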### 13.2. Sample Size, Accrual, and Study Duration:

This study design requires a minimum of 12 and a maximum of 37 evaluable patients. In addition, we expected to accrue an additional 10% to accommodate the potential for problem cases (i.e. patients who are not evaluable for some reason). The first 45 evaluable patients will be used in the decision analysis for this part of the trial, and estimates will also be generated using all evaluable patients. We expect approximately 3 breast cancer patients to be enrolled per month. This will translate to a total of 26 months to accrue a maximum of 50 patients and allowing for the 6 months interim analysis in both Part 1 and Part 2.

The number of patients inevaluable due to screen failure was higher than expected. As such, a total of 50 patients were consented across all sites in order to enroll 37 evaluable patients

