**RPPA:**

For each patient the protein intensity fold-change ratios will be calculated from the RPPA intensity values. Ratios between tumors sampled prior to initiating trametinib single agent treatment and at time of progression on either single agent trametinib or the combination (TOP/pre-treat ratio), will be calculated. These ratios will be median-centered and clustered using Cluster 2.0 software (<http://rana.lbl.gov/EisenSoftware.htm>). Student’s t-test for differences between average protein intensity ratios at these intervals will be calculated using Microsoft Excel by grouping all the ratios for individual clusters.

Table 4	Biomarker Prevalence				
	10%	20%	30%	40%	50%

HR	0.43	0.51	0.55	0.56	0.57
----	------	------	------	------	------

These results and exploratory analyses will be used in planning future studies of this

combination treatment regimen in this patient population. Biomarker analyses on required research biopsies at study entry will be conducted to assess the predictive value of PTEN and other biomarkers on patient outcome. For example, we will assess impact of PTEN status and other markers on survival outcomes as well as ORR and CBR. For survival-based outcomes, Table 4 shows detectable hazard ratios between marker groups for varying prevalence rates and at least 80% power. The Type I error constraint is quite lax in this setting, reflecting a phase II approach and relaxation of constraints but also in the univariate setting can be used to cast a wider net to capture potential markers of interest that may provide insights for the development of future biomarker-driven therapeutic strategies. Fisher exact tests will also be used to identify potential differences in ORR and CBR rates between biomarker groups as well, although depending on prevalence rates we will likely have sufficient power to only detect large differences (e.g. 35%) if we constrain Type I error to 0.05. Again, these will be largely exploratory, and lack of significant results will be viewed with caution given these limitations but will provide

**Table 1: Statistical Considerations for Biomarker Analysis.** Maximum detectable hazard ratios (HR) using one-sided log-rank test with 80% power and alpha=0.2, assuming a sample size of 37, 26 months accrual and 12 months follow-up.

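### Section 13.2 bases the Part 1 decision on 45 evaluable patients, although the design stops at 37 and no cut-off for 45 exists

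*Combined protocol and SAP*

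**What the plan says.** Section 13.2 opens with the size of the design: "This study design requires a minimum of 12 and a maximum of 37 evaluable patients". It adds an allowance: "we expected to accrue an additional 10% to accommodate the potential for problem cases". The next sentence sets the decision population: "The first 45 evaluable patients will be used in the decision analysis for this part of the trial". The paragraph then gives the accrual time: "This will translate to a total of 26 months to accrue a maximum of 50 patients". A closing sentence, in the past tense, reports that "a total of 50 patients were consented across all sites in order to enroll 37 evaluable patients".

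Section 13.3 (Part 1) tests an objective response rate (ORR) of at most 5% against at least 20%, with type I error 10% and power 90%, in a Simon optimal two-stage design. Accrual stops if none of the first 12 evaluable patients responds; otherwise 25 more are added. Success requires "at least 4 patients with clinical response as defined above out of the first 37 evaluable patients accrued", and 3 or fewer is a failure.

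Two other places depend on the sample size. Section 13.3 (Part 2) says "With our planned over-accrual and if all are evaluable, we will have 32 patients available for this portion of the trial", after assuming that about 80% of patients move on to Part 2. The caption to the biomarker power table in Section 13.4 reads "assuming a sample size of 37, 26 months accrual and 12 months follow-up".

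**The concern.** A design with at most 37 evaluable patients has no first 45, so Section 13.2 contradicts itself and Section 13.3. Section 13.2 does not name the part it means, but 12 and 37 are the Part 1 numbers, and Part 2 uses 16 and 32.

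A two-stage rule controls its error rates only when sample size and cut-off are fixed together. Section 13.2 gives a sample size with no cut-off; Section 13.3 gives a cut-off with a different sample size. If more than 37 patients were evaluable, an analyst following Section 13.2 would have only the 4-response cut-off to apply, and would apply it to too many patients. A trial with 3 responses in the first 37 and a fourth among patients 38 to 45 would fail under one section and pass under the other.

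**Working it through.** **Inputs.** p0 = 0.05, p1 = 0.20, stage 1 of 12 patients with a stop at 0 responses, total 37, success at 4 or more (Section 13.3, Part 1); 45, the 10% allowance, 50, 3 patients per month and 26 months (Section 13.2); 80% moving on, and 32 patients (Section 13.3, Part 2).

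**Formula.** With X1 ~ Bin(12, p) and X2 ~ Bin(N − 12, p), the chance of declaring success with cut-off c is

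P = Σ (x = 1 to 12) P(X1 = x) · P(X2 ≥ c − x).

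**Step 1: reproduce the plan's design (N = 37, c = 4).** At p = 0.05:
- x = 1: 0.34128 × 0.12711 = 0.04338
- x = 2: 0.09879 × 0.35762 = 0.03533
- x = 3: 0.01733 × 0.72261 = 0.01252
- x ≥ 4: 0.00224

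The sum is 0.0935. The same sum at p = 0.20 is 0.9024. Both meet the plan. A search over two-stage designs with maximum N from 15 to 49 finds 0/12 then 3/37 to have the smallest expected sample size under the null (23.5), so it is the Simon optimal design for these inputs. The 37 and the cut-off of 4 are correct together.

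**Step 2: look for a source of 45.**
- 37 × 1.1 = 40.7, and 37 / 0.9 = 41.1 (42 when rounded up). Neither is 45.
- Part 2 count: 0.8 × 40 = 32.0 and 0.8 × 41 = 32.8 agree with the stated 32; 0.8 × 45 = 36 does not.
- The biomarker caption uses 37.
- Accrual time, counting both 6-month interim periods in full: 41/3 + 12 = 25.7 months, which agrees with 26; 50/3 + 12 = 28.7 months does not.
- One figure goes the other way: 45 × 1.1 = 49.5, about the stated maximum of 50.

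**Step 3: carry the cut-off of 4 over to a larger set, keeping stage 1 as it is.** At p = 0.05 and N = 45:
- x = 1: 0.34128 × 0.22719 = 0.07754
- x = 2: 0.09879 × 0.49635 = 0.04904
- x = 3: 0.01733 × 0.81597 = 0.01414
- x ≥ 4: 0.00224

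The sum is 0.143.

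| Evaluable N | Cut-off | Type I error | Power |
|---|---|---|---|
| 37 (stated) | ≥ 4 | 9.35% | 90.2% |
| 38 | ≥ 4 | 9.9% | 90.7% |
| 39 | ≥ 4 | 10.6% | 91.1% |
| 41 | ≥ 4 | 11.8% | 91.7% |
| 45 | ≥ 4 | 14.3% | 92.4% |
| 45 | ≥ 5 | 6.0% | 90.6% |

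The 10% limit is first passed at 39 patients.

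**Step 4: chance that the two readings disagree.** Anyone with 4 responses in the first 37 also has 4 in the first 45, so the readings differ only when the fourth response comes after patient 37. At a true ORR of 5% that probability is 14.30% − 9.35% = 4.95 percentage points.

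**The case against.** The strongest reply is that nothing in the plan applies a cut-off of 4 to more than 37 patients. Section 13.3 ties the cut-off to the first 37, so a reader who follows the only complete rule gets 9.35% and 90.2%. The past-tense sentence in Section 13.2 also points to 37 evaluable patients, and then the two readings coincide. Both points stand, and they limit the size of the problem: the inflation is conditional and no calculation in the plan fails.

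They do not remove the contradiction. Section 13.3 contemplates over-accrual in which all patients prove evaluable. It also says that patients who cannot tolerate monotherapy might be replaced yet would still count in the Part 1 decision. Section 13.1.1 defines evaluable in two ways, by one dose or by one cycle plus re-evaluation, so a count of 37 under one definition need not be 37 under the other. The documents therefore do not guarantee that the two sets are the same.

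A second reply is that 45 and 50 form a consistent pair, since 45 plus 10% is about 50. That is true, and may mean that both survive from another design, but this is only an inference. It does not make 45 compatible with the cap of 37 or supply a cut-off.

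**Conclusion.** The concern holds. Section 13.2 names a decision set of 45 that conflicts with the 37-patient maximum in its own paragraph and with the rule in Section 13.3, and no cut-off for 45 is stated. The weight of the other figures (Simon optimality, the Part 2 count, the biomarker caption, the accrual time) shows 37 to be the intended number.

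Under the Section 13.3 rule the error rates are as planned. If more than 37 patients were evaluable and the cut-off of 4 were carried over, type I error would exceed 10% from 39 patients and reach 14.3% at 45. If exactly 37 were evaluable, only clarity is affected.

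These figures assume that stage 2 opens on monotherapy responses among the first 12 evaluable patients. That is the sensible reading, although one sentence in Section 13.3 (Part 1) describes those 12 as treated with the combination. This should be fixed, but it does not undermine the design.

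**What to change.** In Section 13.2:
- Replace 45 by 37 in the sentence on the decision analysis.
- Add that any evaluable patient after the 37th contributes only to the descriptive estimates, which the paragraph already provides for, and not to the go/no-go decision.
- Label 50 as the number consented, distinct from 37 evaluable plus 10% (about 41), and word the accrual sentence to match: 26 months fits about 41 patients at 3 per month with two 6-month interim periods.

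If the sponsor did intend 45, the maximum sample size, cut-off and operating characteristics must all be restated; with the same stage 1, 45 patients would need at least 5 responses (type I error 6.0%, power 90.6%).

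The cost of the main fix is one number and two clarifying sentences in one paragraph. The cut-off, sample size and patients are unchanged.
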